## LIST OF ABBREVIATIONS AND DEFINITION OF TERMS

AE	adverse event
AGM	African green monkey
ALT	alanine aminotransferase
ARA	acid-reducing agent
AST	aspartate aminotransferase
AUC	area under the concentration versus time curve
AUC 0-t	partial area under the concentration versus time curve from time 0 to time t
AUC inf	area under the concentration versus time curve extrapolated to infinite time, calculated as $AUC_{last}$ + $(C_{last}/\lambda_z)$
BID	twice daily
CI	confidence interval
CL cr	creatinine clearance
CL r	renal clearance of unchanged drug in a specific interval ( $CL_r$ (interval)) or cumulatively over all collection intervals
C max	maximum observed concentration of drug
COVID-19	coronavirus disease 2019
СР	conditional power
CSR	clinical study report
СҮР	cytochrome P450 enzyme
DAIDS	Division of AIDS
DDI	drug-drug interaction
DMC	data monitoring committee
ECG	electrocardiogram
eCRF	electronic case report form
EC 50	effective concentration
EDC	electronic data capture
FAM	famotidine
FAS	Full Analysis Set
FDA	Food and Drug Administration
GCP	Good Clinical Practice
Gilead	Gilead Sciences
GMR	geometric mean ratio
IB	investigator's brochure
IC 50	half-maximal inhibitory concentration
ICF	informed consent form
ICH	International Council for Harmonisation (of Technical Requirements for Pharmaceuticals for Human Use)
IEC	institutional ethics committee
IND	investigational new drug

IRB	institutional review board
IRT	interactive response technology
IV	intravenous
LLOQ	lower limit of quantitation
MAV	medically attended visit
MDZ	midazolam
MMRM	mixed-effects model repeated measures
NOAEL	no observed adverse effect level
OATP	organic anion transporting polypeptide
PBMC	peripheral blood mononuclear cell
PCR	polymerase chain reaction
PIT	pitavastatin
P-gp	P-glycoprotein
РК	pharmacokinetic(s)
PROMIS-29	Patient-Reported Outcomes Measurement Information System-29
QD	once daily dosing
RDV	remdesivir (Veklury®)
RNA	ribonucleic acid
RT-qPCR	reverse transcriptase-quantitative polymerase chain reaction
SAC	Safety Assessment Committee
SAE	serious adverse event
SARS-CoV-2	severe acute respiratory syndrome coronavirus 2
SSR	special situation report
t 1/2	terminal elimination half-life
TEAE	treatment-emergent adverse event
ТК	toxicokinetic(s)
ULN	upper limit of normal
UK	United Kingdom
US	United States
WPAI + CIQ: COVID-19	Work Productivity and Activity Impairment + Classroom Impairment Questions: COVID-19 Infection

#### **PROTOCOL SYNOPSIS**

#### Gilead Sciences, Inc. [name]

**Study Title:** A Phase 3, Randomized, Double-Blind, Placebo-Controlled Study to Evaluate the Efficacy and Safety of GS-5245 for the Treatment of COVID-19 in Participants With High-Risk for Disease Progression

**Short Title:** Study of GS-5245 in Participants With COVID-19 Who Have a High Risk of Developing Serious or Severe Illness

IND Number: This is a non-IND study. EudraCT Number: 2022-002741-18 ClinicalTrials.gov Identifier: NCT05603143

#### **Study Centers Planned:**

Approximately 300 centers globally

#### **Objectives and Endpoints:**

Primary Objective(s)			Primary Endpoint(s)			
• To evaluate the efficacy of GS-5245 in reducing the rate of COVID-19–related hospitalization or all-cause death		• Proportion of COVID-19–related hospitalization or all-cause death by Day 29				
Sec	condary Objective(s)	Seconda	ry Endpoint(s)			
•	To evaluate the safety and tolerability of GS-5245 administered in nonhospitalized participants with COVID-19	

(AEs

Incid

	lence of treatment-emergent adverse events s) and laboratory abnormalities lence of serious AEs (SAEs) and AEs ing to study drug discontinuation			
•	To evaluate the efficacy of GS-5245 in reducing all-cause hospitalization		ortion of participants with all-cause italization by Day 29			
•	To evaluate the efficacy of GS-5245 in reducing COVID-19–related medically attended visits (MAVs) or all-cause death	1	ortion of participants with COVID-19– ed MAVs or all-cause death by Day 29			
•	To evaluate the efficacy of GS-5245 in reducing COVID-19–related MAVs		ortion of participants with COVID-19– ed MAVs by Day 29			
•	To evaluate the efficacy of GS-5245 in reducing all-cause death	
 
Prop Day
 
	ortion of participants with all-cause death by 29			

•	To evaluate the efficacy of GS-5245 in reducing the duration and severity of COVID-19 symptoms	•	Time to COVID-19 symptom alleviation by Day 15
•	To evaluate the antiviral activity of GS-5245 on SARS-CoV-2 nasal swab viral load at Day 5	•	Change from baseline (Day 1) in SARS-CoV-2 nasal swab viral load at Day 5
•	To evaluate the plasma pharmacokinetic(s) (PK) of GS-441524 (metabolite of GS-5245)	•	Plasma concentrations and PK parameters $AUC_{tau}$ , $C_{tau}$ , and $C_{max}$ of GS-441524, as available

**Study Design:** This Phase 3 study will be a randomized, double-blind, placebo-controlled study comparing the safety and efficacy of oral GS-5245 with placebo in nonhospitalized participants with COVID-19 who are at high risk of progression to hospitalization.

After screening procedures, eligible participants may be randomized in a 1:1 ratio to receive GS-5245 or placebo.

Randomization will be stratified by duration of symptoms at enrollment ( $\leq$  3 days versus > 3 days), and vaccination status (ever versus never).

#### Number of Participants Planned:

Approximately 2300 participants will be randomized into this study. Up to 3150 participants may be enrolled depending on the sample size re-estimation result.

**Target Population:** Nonhospitalized participants with COVID-19 with at least 1 risk factor (if unvaccinated) and at least 2 risk factors (if vaccinated at any point) for disease progression.

Duration of Intervention: Participants will receive oral GS-5245 or placebo for 5 days.

#### **Diagnosis and Main Eligibility Criteria:**

Participants must meet all the following inclusion criteria to be eligible for participation in this study:

- 1) Aged  $\geq$  18 years at screening.
- 2) Willing and able to provide written informed consent, or with a legal representative who can provide informed consent (where locally and nationally approved).
- 3) SARS-CoV-2 infection confirmed by PCR or an approved alternative assay (eg, Rapid Antigen Test) ≤ 5 days before randomization. Serologic tests will not be accepted.
- 4) Initial onset of COVID-19 signs/symptoms ≤ 5 days before randomization with ≥ 1 of the following targeted signs/symptoms present at randomization:
  - a) Stuffy or runny nose.

- b) Sore throat.
- c) Shortness of breath (difficulty breathing).
- d) Cough.
- e) Low energy or tiredness.
- f) Muscle or body aches.
- g) Headache.
- h) Chills or shivering.
- i) Feeling hot or feverish.
- j) Nausea.
- k) Vomiting.
- l) Diarrhea.
- 5) Not currently hospitalized or requiring hospitalization.
- 6) Presence of  $\geq 1$  risk factor (if unvaccinated) or  $\geq 2$  risk factors (if vaccinated at any point) for progression to severe disease. Risk factors are the following:
  - a) Aged  $\geq$  50 years.
  - b) Current or recent ( $\leq 6$  months prior to randomization) cancer (other than localized skin cancer).
  - c) Have human immunodeficiency virus infection.
  - d) Prior splenectomy.
  - e) Prior solid organ, stem cell, or bone marrow transplant.
  - f) Have systemic rheumatologic or dermatologic disorders.
  - g) Use of systemic immunosuppressive agents, eg, high-dose corticosteroids (ie,  $\geq 20$  mg of prednisone or equivalent per day administered for  $\geq 2$  weeks), alkylating agents, antimetabolites, transplant-related immunosuppressive drugs, cancer chemotherapeutic agents classified as severely immunosuppressive, tumor necrosis factor blockers, other biologic agents that are immunosuppressive or immunomodulatory.
  - h) Have cerebrovascular disease.

- i) Have cardiovascular disease, including heart failure, coronary artery disease, cardiomyopathies, and hypertension.
- j) Have chronic kidney disease (provided participant does not meet exclusion criterion 7).
- k) Have chronic lung disease (interstitial lung disease, pulmonary embolism, pulmonary hypertension, bronchiectasis, or chronic obstructive pulmonary disease).
- 1) Have chronic liver disease.
- m) Have cystic fibrosis.
- n) Have diabetes mellitus, type 1 and/or type 2.
- o) Have neurodevelopmental and/or neurodegenerative conditions.
- p) Have a body mass index  $\geq 25$  kg/m^2.
- q) Have sickle cell disease.
- r) Have primary immunodeficiencies.
- s) Have compensated cirrhosis.
- t) Have asthma.
- u) Have  $\geq 20$  pack-year smoking history and currently smoking or have quit within the past 15 years.

Exclusion criteria for participation include:

- Anticipated access to and use of authorized or approved COVID-19 therapies during the current COVID-19 illness < 5 days after randomization (therapies include nirmatrelvir/ritonavir, molnupiravir, ensitrelvir, intravenous remdesivir [RDV, Veklury®], monoclonal antibodies).
- 2) Received any approved, authorized, or investigational direct-acting antiviral drug against SARS-CoV-2 for the treatment of COVID-19 < 28 days or < 5 half-lives, whichever is longer, before randomization.
- 3) Anticipated need for hospitalization < 48 hours after randomization.
- 4) New oxygen requirement < 24 hours before randomization.
- 5) Known influenza or any other suspected or confirmed concurrent active systemic infection other than COVID-19 that may interfere with the evaluation of response to the study drug.

- 6) Decompensated cirrhosis (Child-Pugh class B or class C) or acute liver injury/failure.
- 7) Undergoing dialysis, or known history of moderate or severe renal impairment, or known  $CL_{cr} < 60 \text{ mL/min}$  (as calculated by Cockroft-Gault) or eGFR < 60 mL/min/1.73m^2 within the last 6 months. Potential participants meeting the laboratory criterion may be enrolled if test results available before dosing show that renal function no longer meets this criterion.
- 8) Known history of any of the following abnormal laboratory results (< 6 months before randomization) unless confirmed as resolved to not meet criteria at screening.
  - a) Alanine aminotransferase (ALT)  $\geq$  5 × upper limit of normal (ULN).
  - b) Bilirubin  $\ge 2 \times ULN$  ( $\ge 3 \times ULN$  for participants with Gilbert's syndrome).
- 9) Positive urine pregnancy test at screening.
- 10) Breastfeeding (nursing).
- 11) Unwilling to use protocol-mandated birth control.

12) Known hypersensitivity to the study drug, its metabolites, or formulation excipient.

- 13) Requirement for ongoing therapy with or prior use of any prohibited medications.
- 14) Received an approved, authorized, or investigational COVID-19 vaccine (including booster dose) < 120 days before randomization.
- 15) Any inability to take study drug or comply with study procedures that, in the opinion of the investigator, would make the participant unsuitable for the study.

#### **Study Procedures/Frequency:**

- Screening: within 48 hours of the baseline visit (screening visit can be the same as day as the baseline visit).
- Study treatment period: Day 1 (baseline) to Day 5.
- Posttreatment follow-up: Up to 29 days (+ 5 days) after the first dose of study drug (in-person or virtual).

The schedule of study procedures is presented in Table 1.

## Test Product, Dose, and Mode of Administration:

GS-5245 350 mg ( $1 \times 350$  mg tablet) administered orally **twice daily** without regard to food with approximately 240 mL of water for 5 days.

#### Reference Therapy, Dose, and Mode of Administration:

Placebo administered orally **twice daily** without regard to food with approximately 240 mL of water for 5 days.

#### **Statistical Methods:**

A total of 2300 participants provides > 90% power to detect a ratio of 0.25 (GS-5245 to placebo in the primary endpoint [proportion of COVID-19–related hospitalization or all-cause death by Day 29], which is equal to a hazard ratio of 0.25) using a 2-sided significance level of 0.05 assuming the event rate is 2% in the placebo group.

[figure not shown]
The primary endpoint will be analyzed using a Cox proportional hazards model with the stratification factors (duration of symptoms and vaccination status) as covariates. The hazard ratio and 95% CI will be provided.

A gatekeeping approach will be used for testing the key secondary endpoints. The endpoints will be tested in the following sequential order:

- Proportion of participants with all-cause hospitalization by Day 29.
- Proportion of participants with COVID-19-related MAVs or all-cause death by Day 29.
- Proportion of participants with COVID-19-related MAVs by Day 29.
- Proportion of participants with all-cause death by Day 29.

An unblinded interim analysis of efficacy and futility is planned after 50% of planned participants complete the Day 29 assessment or prematurely discontinue from the study, or 50% of expected primary endpoint events occur, whichever comes first. If the interim is triggered by 50% of enrollment, an additional unblinded interim analysis may be conducted after 50% of expected events have occurred. The unblinded interim analysis at 50% of expected events will include a sample size re-estimation.

#### **STUDY SCHEMA**

COVID-19 = coronavirus disease 2019; D = Day

- a Access determined at the site level by the principal investigator and participant.
- b Effective COVID-19 antiviral therapies such as nirmatrelvir/ritonavir, molnupiravir, ensitrelvir, intravenous remdesivir, monoclonal antibodies, or any other locally authorized/approved direct-acting therapy against SARS-CoV-2.

#### **STUDY PROCEDURES TABLE**

## Table 1.Study Procedures Table

Study Visit	Screening a	Baseline/ Day 1 a, b	Day 3 b	Day 5 b	Day 10	Day 15 b	Day 29	Early Discontinuation Visit b
Visit Window			± 1 d	ay c	± 2	days	+ 5 days	
Visit Type	In Pe	In Person d		In Person d	In Person d or Virtual e			In Person d
Written informed consent	X							
Medical history f	Х							
Document SARS-CoV-2 infection	Х							
Complete physical examination g	Х	X		X				Х
Symptom-directed physical examination			X			X		
Height and weight	Х							
Vital signs h	Х	X	X	X	X	X	X	Х
Screening ALT, bilirubin, serum creatinine, and $CL_{cr}/eGFR^{i}$	X							
Chemistry, coagulation, and hematology panels j		X	X	X		X		Х
Urine or serum pregnancy tests k	Х	X				X		Х
Mid-turbinate nasal swab l		X	X	X	X	X		Х
SARS-CoV-2 serology		X						
CCI								
CCI								
MAV information/oxygen supplementation requirement o		X	X	X	X	X	X	Х

Study Visit	Screening a	Baseline/ Day 1 a, b	Day 3 b	Day 5 b	Day 10	Day 15 b	Day 29	Early Discontinuation Visit b
Visit Window			± 1 d	ay c	± 2	days	+ 5 days	
Visit Type	In Person d		In Person d or Virtual e	In Person d	In Person d or Virt		rtual e	In Person d
COVID-19 Symptom Questionnaire p		X	X	X	X	X	Х	Х
PROMIS-29		X				X	Х	Х
WPAI + CIQ: COVID19		X				X	Х	Х
Study drug dispensation		X						
Study drug dosing (GS-5245 or placebo)		X	X	X				
Study drug bottle return q				X	X	X	Х	Х
Adverse events and concomitant medications	Х	X	X	Х	X	X	Х	Х

ALT = alanine aminotransferase;  $CL_{cr}$  = creatinine clearance; COVID-19 = coronavirus disease 2019; ED = early discontinuation; eGFR = estimated glomerular filtration rate; MAV = medically attended visit; PCR = polymerase chain reaction; PK = pharmacokinetic(s); PROMIS-29 = Patient-Reported Outcomes Measurement Information System-29; RT-qPCR = reverse transcriptase-quantitative polymerase chain reaction; SARS-CoV-2 = severe acute respiratory syndrome coronavirus 2; WPAI + CIQ:COVID19 = Work Productivity and Activity Impairment + Classroom Impairment Questions: COVID-19 Infection

a Screening window is within 48 hours of the Day 1 visit. Day 1 visit may occur on the same day as screening. If the Day 1 and screening visits are the same day, do not repeat physical exam and vital signs.

- b Laboratory tests for safety will be performed on Days 1 and 5, on Days 3 and 15 when an in-person visit is conducted, and at early discontinuation.
- c Day 3 and Day 5 visits should be conducted on separate calendar days.
- d In-person is defined as a visit at a medical facility or elsewhere by a health care provider (where permitted).
- e Virtual visit is defined as an interaction with a health care professional using telephone or online-based interaction (eg, telehealth, webcast, video conferencing).

f Medical history will include the date of first COVID-19 symptoms, overall COVID-19 symptoms, all COVID-19 vaccinations prior to screening, exposure source, demographics, baseline characteristics, allergies, and all other medical history.

- g A complete physical examination must include source documentation of general appearance and the following body systems: head, neck, and thyroid; eyes, ears, nose, throat, mouth, and tongue; chest (excluding breasts); respiratory; cardiovascular; lymph nodes, abdomen; skin, hair, nails; musculoskeletal; and neurological. For participants with compensated cirrhosis, a complete physical exam must also include a clinical assessment of ascites (absent, slight, or moderate) and a clinical assessment of hepatic encephalopathy (Absent, Grade II, Grade III, or Grade IV), as described in Section 6.3.2.1. Urogenital and reproductive examination should only be completed if clinically indicated.
- h Vital signs include heart rate, respiratory rate, temperature, oxygen saturation, and blood pressure. Vital signs are collected at in-person visits only.
- i Screening: Serum ALT, bilirubin, serum creatinine, and CLcr/eGFR assessments at screening (prior to dosing) are not required unless deemed necessary by the investigator to confirm eligibility, using a local laboratory. See Appendix 11.4 for country-specific requirements.
- j All required baseline laboratory assessments should be collected prior to first study drug dose.

- k At screening, a urine pregnancy test will be performed at the local laboratory for participants assigned female at birth and of childbearing potential. On Day 1, Day 15, and ED visits, these participants will have a serum pregnancy test performed via the central laboratory for in-person visits or a urine pregnancy test for virtual visits. At screening, a follicle-stimulating hormone test is required to confirm the postmenopausal state in participants younger than 54 years, who have stopped menstruating for at least 12 months but do not have documentation of ovarian hormonal failure, as described in Appendix 11.3
- 1 A mid-turbinate nasal swab will be collected at in-person visits and used for SARS-CoV-2 RT-qPCR, potential multiplex viral PCR, potential infectious viral titer assessment, and potential resistance testing. The nasal swab must be collected by clinic/study personnel in person. For virtual visits on Days 3, 10, or 15 no samples will be collected.

- Medically attended visit information includes any interactions with health care professionals other than study staff or designees including hospitalization; in-person emergency, urgent, or primary care visits; or any other in-person visit attended by the participant and a health care professional. The nature and cause of the visit should be identified. Medically attended visit information and oxygen supplementation information should be collected through Day 29.
- p The COVID-19 symptom questionnaire should be completed daily (at approximately the same time each day) from predose (prior to first dose on Day 1) through Day 15, and on Day 29. If a participant discontinues from the study early, the participant should complete this questionnaire during the early discontinuation visit.
- q Study drug bottle should be returned by the participant on Day 5, if the participant has already completed both doses of study drug. If the participant has study drug at the end of the Day 5 visit, the participant may return the study drug bottle on Day 10. If the Day 10 visit is virtual, drug accountability should be performed virtually and the participant will be instructed on returning the study drug bottle.

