6. EFFICACY ANALYSES

6.1. Primary Efficacy Endpoint

6.1.1. Definition of the Primary Efficacy Endpoint

The primary endpoint of the study is the proportion of COVID-19–related hospitalization or all-cause death by Day 29. The endpoint will be derived by combining the available all-cause death and COVID-19–related hospitalization reported by the site.

COVID-19–related hospitalization is defined as \geq 24 hours of acute care for a reason related to COVID-19, in a hospital or similar acute care facility, including emergency rooms or temporary facilities instituted to address medical needs of those with COVID-19. This includes specialized acute medical care units within an assisted living facility or nursing home. This does not include hospitalization for the purposes of public health and/or clinical study execution. The date and duration of hospital admission, and primary reason for hospitalization (including if the hospitalization is related to COVID-19) will be recorded.

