6.2. Secondary Endpoints

Key Secondary Efficacy Endpoints

The alpha-controlled secondary endpoints include the following:

- Proportion of participants with all-cause hospitalization by Day 29
- Proportion of participants with COVID-19–related MAVs or all-cause death by Day 29
- Proportion of participants with COVID-19-related MAVs by Day 29
- Proportion of participants with all-cause death by Day 29

Medically attended visits are defined as any interactions with health care professionals other than study staff or designees including hospitalization; in-person emergency, urgent, or primary care visits; or any other in-person visit attended by the participant and a health care professional.

Other Secondary Efficacy Endpoints

- Time to COVID-19 symptom alleviation by Day 15
- Change from baseline (Day 1) in SARS-CoV-2 nasal swab viral load at Day 5

Symptom alleviation is defined as all targeted symptoms measured via the SIC questionnaire (Appendix 2) with a rating of 0, or at least 3 points decrease in rating from baseline, or an answer "No" to the question for at least 48 consecutive hours. A new version of the questionnaire that measures COVID-19 symptoms, COVID-19 Symptom Questionnaire, was introduced in protocol Amendment 1 but was not available to any participant by the time of stop of enrollment. Data for the COVID-19 Symptom Questionnaire were not collected.

Targeted symptoms are those listed below:

- Nasal congestion (stuffy nose)
- Runny nose
- Sore throat

- Shortness of breath (difficulty breathing)
- Cough
- Feeling generally unwell (run down)
- Fatigue (tiredness)
- Physical weakness
- Feeling faint
- Muscle aches/pains
- Joint aches/pains
- Headache
- Chills
- Uncontrollable body shaking/shivering
- Fever

The first day of the 48 consecutive hours will be considered the symptom alleviation date. The date and time stamps at which participants complete the questionnaire each day are captured in electronic diary as "Form Saved Time" and will be used to determine whether the requirement of 48 continuous hours is satisfied.

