Proportion of participants with negative SARS-CoV-2 nasal swab viral load at Days 3, 5, 10, and 15	Participants in the Virology analysis set who had SARS-CoV-2 nasal swab collected and nonmissing result of viral load reported at selected visits	Number of participants with negative SARS-CoV-2 nasal swab viral load
Proportion of participants with negative SARS-CoV-2 infectious viral titer at Days 3, 5, 10, and 15	Participants in the Virology analysis set who had SARS-CoV-2 nasal swab collected and nonmissing result of SARS-CoV-2 infectious viral titer reported at selected visits	Number of participants with negative SARS-CoV-2 infectious viral titer

4) Definition of Hospitalization

MAVs type of Emergency Room, non-ICU Hospitalization, ICU Hospitalization, and Hospitalization (unknown ward) could meet criteria for hospitalization if one of the following conditions is met:

- If the duration of the MAV is greater than 24 hours.
- If the duration is missing and end date of the MAV is 1 day after the start date.

Time to hospitalization is calculated as Start date of Hospitalization – First dose date + 1.

5) SARS-CoV-2 positive at baseline

SARS-CoV-2 positive at baseline is defined as test result from central lab.

- Cepheid's Xpert Xpress CoV-2/Flu/RSV plus (Multiplex) test result is positive for SARS-CoV-2 or
- SARS-CoV-2 RT-qPCR test result is numerical viral load result or "<2228cp/mL SARSCoV2 detected", regardless the sample was collected with less than specified volume of test solution.

GS-US-611-6273-Final Analysis-SAP-v1.0

ELECTRONIC SIGNATURES

Signed by	Meaning of Signature	Server Date (dd-MMM- yyyy hh:mm:ss)
PPD	Biostatistics eSigned	24-Jan-2024 01:01:34
PPD	Global Development Lead (GDL) eSigned	24-Jan-2024 17:55:34

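### The SAP's programming rule for hospitalization lists four visit types and omits settings that the endpoint definition counts, so qualifying stays could be missed in the primary endpoint and all-cause hospitalization

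*Protocol*

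**What the plan says.** **Endpoint definition.** Protocol 8.5.1 and SAP 6.1.1 define a COVID-19-related hospitalization as at least 24 hours of acute care in a hospital or comparable acute facility, "including emergency rooms or temporary facilities instituted to address medical needs of those with COVID-19". SAP 6.1.1 adds: "This includes specialized acute medical care units within an assisted living facility or nursing home". Protocol 8.5.2 uses the same settings for all-cause hospitalization, the first key secondary endpoint. Neither definition limits who provides the care.

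**Source of the data.** SAP 6.1.1 says: "The endpoint will be derived by combining the available all-cause death and COVID-19–related hospitalization reported by the site". Appendix 3 item 4 supplies the programming rule: "MAVs type of Emergency Room, non-ICU Hospitalization, ICU Hospitalization, and Hospitalization (unknown ward) could meet criteria for hospitalization", subject to a duration condition. No other derivation of hospitalization is given.

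**MAV definition.** Protocol Table 1 footnote o describes the MAV information to be collected as "any interactions with health care professionals other than study staff or designees including hospitalization". SAP 6.2 reads: "Medically attended visits are defined as any interactions with health care professionals other than study staff or designees including hospitalization". Protocol 6.3.2.7 and 8.5.2 agree with both.

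**Cross-checks.** Protocol 7.1.2 makes in-patient hospitalization an SAE criterion. SAP 7.1.4 reconciles SAEs in the clinical database with the safety database. Nothing compares MAV-derived hospitalizations with hospitalization SAEs.

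**The concern.** A programming specification should carry out the endpoint definition, and here it is narrower. Two settings that the definition names have no counterpart among the four types, and no text says under which type a site should record them. If a site uses a type outside the four, a stay that meets the definition is not counted.

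Two endpoints are exposed: the primary endpoint, and all-cause hospitalization, which comes first in the testing sequence. Capture would also depend on local facilities and coding habits across about 300 planned centers. In a blinded trial there is no reason to expect this to differ by arm, so the main cost is lost events and precision rather than a biased hazard ratio. It still matters in a trial whose enrollment was stopped because the primary event rate was lower than expected (SAP 2.3).

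**Working it through.** **1. Definition against rule**

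| Setting in Protocol 8.5.1 and SAP 6.1.1 | Type named in Appendix 3 item 4 |
|---|---|
| Hospital | ICU, non-ICU or unknown-ward hospitalization |
| Emergency room | Emergency room |
| Temporary COVID-19 facility | None named |
| Acute unit in assisted living facility or nursing home | None named |

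**2. Which endpoints depend on the rule**

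- Primary endpoint: its hospitalization component does. Deaths enter separately, so a participant whose stay was missed but who dies by Day 29 is still an event, dated at death.
- All-cause hospitalization: depends on it fully.
- COVID-19-related MAVs, with or without death: not affected, since any MAV type counts.
- All-cause death: not affected.

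A participant moved from an unlisted facility to a hospital still counts if the hospital stay qualifies, but with a later event date, because item 4 times the event from the start of the hospitalization.

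**3. The plan's own power figure**

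Inputs from SAP 1.2 and 1.3: 2300 participants randomized 1:1, so n = 1150 per arm; placebo rate 0.02; ratio 0.25, so active rate 0.005; two-sided 0.05. The mean rate is 0.0125.

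Two-proportion power = Φ{[0.015·√1150 − 1.96·√(2·0.0125·0.9875)] / √(0.02·0.98 + 0.005·0.995)} = Φ(1.280) = 90.0%.

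The same method needs 2302 participants for 90% power. SAP 1.3 states about 90% with 2300, so the figure reproduces. On the same inputs the Freedman log-rank form gives 89.6% and the Schoenfeld form 96.1%.

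**4. What one missed event is worth**

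- Expected events at full size: 1150 × (0.02 + 0.005) = 28.75. One event is 1/28.75 = 3.5% of the information.
- SAP 2.3 reports that fewer than 50% were randomized, which is fewer than 1150 (SAP 6.5). At the planned rates that gives fewer than 575 × 0.025 = 14.4 events, so one event is about 1/14.4 = 7% or more.

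**5. Sensitivity at full size**

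The documents give no fraction of stays in unlisted settings. The losses below are assumptions, equal in both arms, so the ratio stays at 0.25.

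| Assumed share of events missed | Expected events | Power, two proportions | Power, Schoenfeld |
|---|---|---|---|
| 0% | 28.75 | 90.0% | 96.1% |
| 5% | 27.3 | 88.4% | 95.2% |
| 10% | 25.9 | 86.7% | 94.1% |
| 20% | 23.0 | 82.5% | 91.4% |

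**The case against.** The strongest reply is that no loss is shown. The eCRF is not in the documents, and a site could record a stay in a temporary facility or nursing-home unit as an emergency room visit or an unknown-ward hospitalization. SAP 6.1.1 also refers to hospitalization as the site reports it, and item 4 says the four types could qualify without saying that only they can. This stands as far as size is concerned: the number of affected stays is unknown and may be zero. It does not close the gap, because item 4 is headed as the definition of hospitalization, is the only derivation given, and leaves two named settings unassigned.

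A reader might infer something stronger: that excluding study staff from the MAV definition removes care given by the investigator from the primary and MAV endpoints. The documents do not support this. The exclusion is part of the MAV endpoints' own definition, stated consistently in both documents, so those endpoints lose nothing they were meant to include. The same sentence names hospitalization as included, so an ordinary admission is recorded. Whether an MAV should include unscheduled care by site staff is a debatable preference. Changing it would redefine two alpha-controlled endpoints and require a protocol amendment. Nor can a power loss be put on the MAV endpoints: the documents give neither a planned power for them nor a share of contacts made with site staff, and a participant seen first at the site and later elsewhere still counts.

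**Conclusion.** The concern holds in a limited form. Appendix 3 item 4 is narrower than the hospitalization definition it should implement, and no written check would detect a missed stay. The exposure is confined to the hospitalization component of the primary endpoint and to all-cause hospitalization.

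The size rests on two things. The first is the planned rates of 2% and 0.5%, under which each missed event is about 3.5% of the information at 2300 participants and about 7% or more below 1150. The second is how many stays fall outside the four types, which the documents do not allow one to estimate. This is a gap in the specification that should be closed, not evidence that events were lost. It is not a general problem with the key secondary endpoints.

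**What to change.** In SAP Appendix 3 item 4, apply the SAP 6.1.1 hospitalization definition to every MAV type. Name temporary COVID-19 facilities and acute units in nursing homes or assisted living as qualifying settings. State that a qualifying stay counts whoever provides the care; this is a clarification and leaves the MAV definition unchanged. Using the full definition also settles two nearby differences in item 4: the duration test "If the duration of the MAV is greater than 24 hours", where the definition says at least 24 hours, and the missing-duration rule "If the duration is missing and end date of the MAV is 1 day after the start date", which read literally leaves out longer stays.

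Before unblinding, compare MAV-derived hospitalizations with SAEs reported under the hospitalization criterion and resolve mismatches blinded. The SAE criterion has no 24-hour minimum and may not cover every nursing-home unit, so each mismatch should be judged against the 6.1.1 definition. The comparison supplements the wording change and does not replace it.

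The cost is a SAP wording change and one blinded data reconciliation. No protocol amendment and no new data collection from participants are needed.
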